10. Patients will be instructed to use a cotton-tipped applicator to apply petroleum jelly only to the side of their wound without tissue glue two times a day for one week following surgery.
11. After suture removal, tissue glue will be re-applied to both halves of the wound.
12. We plan to enroll 70 wounds in the study in order to detect a difference of 4 on the Patient Observer Scar-Assessment Scale, since the scale is based on a 60-point system. We calculated that we would need to enroll at least 40 subjects using an assumed standard deviation of 7.6,

alpha of 0.05, and a power of 90. However, due to the length of the study we expect a dropout rate of approximately 40%.

13. Wounds will be evaluated at 3 month and 6 month follow-ups. These time points were chosen due to the ability to see differences in surgical interventions at these time points, while differences in surgical interventions are more difficult to distinguish over time. In addition, study quality will decrease over time since patients will be more likely to drop out of the study.
14. The efficacy of intervention methods will be assessed at the 3 month and 6 month follow-ups by having the patient and two blinded observers rate the healing progression of the wound using the POSAS. The observers will be either dermatology faculty or dermatology. The POSAS is a standard metric in measuring wound healing in cutaneous surgery studies since it does not require training but takes into account the scar assessment of the patient and observers. Subsequently, the height and width of the scar will be measured and compared to the surrounding unaffected skin. The assessments of the two blind observers will be averaged. Data will be managed using REDCap, a World Wide Web-based data collection page. All adverse events and any complications will be consistently monitored and recorded for each side of the scar.
15. After the patients have their scar observed at the 3 month and 6 month follow-ups, they will be financially compensated for their travel and participation in the study. Patients will be paid \$50 for each visit, potentially earning a total of \$100 for their participation in the study. This money will be provided by funds from the WVU Department of Dermatology. Patients will be asked to provide their Social Security Number and verification of U.S Citizenship or Permanent Resident Status to receive payment.

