16. We will use a paired Wilcoxon test to compare the mean POSAS scores for the two wound closure techniques at 3 and 6 months after surgery. To compare differences in scar height, width, and depth between the two closure techniques at the 3 and 6 month follow-ups paired Wilcoxon tests will be used. McNemar tests will be used to calculate differences in the proportion of scars with measurable heights and depths between the two wound closure techniques. This will help account for instances where patients have a scar height and depth of zero. R statistical computing software will be used to run statistical analyses (R Foundation for Statistical Computing, Vienna, Austria). The intent-to-treat principle will be used to compute the study outcomes.

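### POSAS is tested unadjusted at both 3 and 6 months, with no deciding visit or score named, although the sample size corresponds to one two-sided comparison at alpha 0.05.

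*Combined protocol and SAP*

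**What the plan says.** All references are to numbered items in the Clinical Protocol of the combined protocol and SAP.

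- **Item 12 (sample size)** plans to "detect a difference of 4 on the Patient Observer Scar-Assessment Scale", with an assumed SD of 7.6 and an "alpha of 0.05, and a power of 90". This gives at least 40, raised to 70 wounds for about 40% dropout. No visit and no rater is attached to the 4 points or to the SD.
- **Item 13 (timing)**: "Wounds will be evaluated at 3 month and 6 month follow-ups". Both are justified together and neither is called primary.
- **Item 14 (assessment)** measures efficacy at both visits by "having the patient and two blinded observers rate the healing progression of the wound using the POSAS". It then says: "The assessments of the two blind observers will be averaged". It gives no rule for joining or ranking the patient and observer scores.
- **Item 16 (analysis)** specifies a "paired Wilcoxon test to compare the mean POSAS scores for the two wound closure techniques at 3 and 6 months after surgery". It adds paired Wilcoxon tests for scar height, width and depth, and McNemar tests for measurable height and depth. It gives no order of testing and no adjustment.

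**The concern.** A power statement at alpha 0.05 refers to one defined test. Here the analysis has at least two candidates for that test, one per visit. It has more if the patient and observer scores may each be analysed alone. The plan has no success rule, so the 5% error rate behind item 12 is attached to no particular result.

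Two things are at stake. First, if a significant result at one visit is enough, the chance of a false claim exceeds 5%. Second, if visit and score are chosen once the data are known, nobody can show afterwards that the choice was independent of the results.

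**Working it through.** **Inputs.** From item 12: difference 4, SD 7.6, alpha 0.05, power 90%, n = 40, 70 wounds, about 40% dropout. From item 16: paired Wilcoxon test at each of two visits. Not in the plan, so assumed: two-sided testing; 7.6 is the SD of the within-wound paired difference; normal differences; independent wounds; between-visit correlation r of the paired differences.

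**Step 1. Reproduce the 40.** Normal approximation for one paired comparison: n = [SD × (z₀.₉₇₅ + z₀.₉₀) / difference]² = [7.6 × (1.960 + 1.282) / 4]² = 37.9, so 38. The exact paired t calculation (noncentral t, standardised difference 4/7.6 = 0.526) gives 89.3% power at 39 pairs and 90.1% at 40, so 40 is reproduced.

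Alternatives do not fit:

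| Calculation | n |
|---|---|
| Paired t, one-sided 0.05 | 33 |
| Two independent groups, two-sided 0.05 (normal) | 76 per group |
| Paired t, two-sided 0.025 (alpha split over two visits) | 48 |

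The plan's number therefore corresponds to one two-sided paired comparison, with no alpha set aside for a second.

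**Step 2. Error rate under the two possible success rules.** Take two two-sided 0.05 tests whose statistics are bivariate normal with correlation r:

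- Either visit suffices: error = 1 − P(|Z₁| < 1.96 and |Z₂| < 1.96). At r = 0 this is 1 − 0.95² = 9.75%.
- Both visits required: error = 0.05 + 0.05 − (either-visit error). At r = 0 this is 10% − 9.75% = 0.25%.

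| Assumed r | Either visit | Both visits |
|---|---|---|
| 0 | 9.75% | 0.25% |
| 0.5 | 9.07% | 0.93% |
| 0.7 | 8.35% | 1.65% |
| 0.9 | 7.04% | 2.96% |

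Simulated paired Wilcoxon tests with 42 pairs gave 9.5%, 9.2%, 8.4% and 7.0% for the either-visit rule, so the normal figures carry over to the planned test.

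**Step 3. Power if one primary is named.** Expected pairs: 70 × 0.6 = 42. The planned test is the Wilcoxon, so its power is the relevant one; it was obtained by simulation with normal differences.

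| Pairs | Paired t, 0.05 | Paired Wilcoxon, 0.05 |
|---|---|---|
| 40 | 90.1% | about 88.7% |
| 42 | 91.5% | about 90% |

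With a single named primary, the 70 wounds still deliver the planned power for the planned test.

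**The case against.** The strongest reply is that item 16 only lists a comparison at each visit. It nowhere says that a result at one visit is enough. A reader might infer that the plan has an inflated error rate. The documents do not support that: the inflation appears only under an either-visit rule, and under a both-visits rule the test is conservative. The 9.75% also needs two ratings of the same scar, three months apart, to be independent, which is hard to believe; with r between 0.7 and 0.9 the excess over 5% is 2 to 3.3 points. This part of the objection stands. What is shown is a missing rule, with inflation as one of its possible consequences.

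Item 12 does not itself say one test, two-sided, paired, or SD of the difference. These are inferred because they reproduce 40. The inference is strong, but it is not the plan's wording.

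A reader might also infer that the patient's score is unblinded, so that the conclusion could rest on a biased rating. In the first week patients are told to "apply petroleum jelly only to the side of their wound without tissue glue", so they can then tell the halves apart, and item 14 calls only the observers blinded. But after suture removal "tissue glue will be re-applied to both halves of the wound", and no item states what the patient knows at 3 or 6 months. Unblinding at rating is an inference and carries no weight in the conclusion here.

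Finally, item 14 favours POSAS partly because it reflects both patient and observer views. That is a fair argument against insisting on the observer score, and it stands.

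**Conclusion.** The gap is real. Items 12 to 16 name no deciding visit, deciding POSAS score, order of testing or adjustment, while the sample size corresponds to one two-sided paired comparison at 0.05. Running both tests as written, with the score left open, does not secure the single-test alpha behind item 12.

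The size depends on a rule that the plan does not state: 7.0% to 9.75% if either visit may support the claim, over assumed correlations from 0.9 down to 0, and 3.0% or less if both are required. These figures are for one score. Testing patient and observer scores separately under an either-result rule would raise the error further, but the plan does not say that this will be done.

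It would also be wrong to infer that the trial must be enlarged. An alpha split evenly over the visits would need 48 pairs (48 / 0.6 = 80 wounds) for 90% paired-t power at each visit separately, and more with the Wilcoxon test, but a single named primary avoids this. The scar-dimension and McNemar tests add to the count of tests, but the point does not rest on them.

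**What to change.** Before any results are seen:

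1. In item 16, name one primary POSAS score at one visit, tested two-sided at 0.05 with the planned paired Wilcoxon test. The choice of visit is the sponsor's. The averaged observer score is a reasonable choice because only the observers are described as blinded; a combined patient and observer score, defined in advance, would also close the gap.
2. Test the same score at the other visit at 0.05 only if the primary is significant.
3. Treat the remaining POSAS scores and the scar-dimension and McNemar tests as secondary.
4. In item 12, confirm that the 4-point difference and the SD of 7.6 apply to the named score and that 7.6 is the SD of the paired difference. If not, justify new values and restate the power.

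**Cost.** Wording in items 12 and 16 only; the 40 pairs and 70 wounds stay as they are. That is conditional on three things: the item 12 inputs hold for the named score; wounds can be treated as independent, although item 5 allows up to three per patient; and dropout is 40% at the chosen visit, although item 13 expects it to grow with time. The downside is that the other visit, or another score, cannot carry the conclusion if the primary fails.
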